### 2.3 Exploratory Objectives

- To explore predictors of biomarker response and mechanisms of resistance based on exploratory analysis of tumor tissue obtained through biopsies
  - a) Levels of PTEN expression by immunohistochemistry (IHC) and qPCR
  - b) Presence of mutations in the PIK3CA gene
  - c) HER2 (IHC, FISH) and ER/PR levels (IHC) in tumor biopsy from a metastatic site.

- d) Levels of MEK activity measured by phosphorylated p-ERK1/2 (IHC) and phosphorylated p-S6 (S235/236 and S240/244) at baseline and upon progression of disease
  - e) Levels of phosphorylated p-AKT (IHC) at baseline and upon progression of disease
  - f) Gene expression profiling to assign a triple negative subtype
  - g) Whole exome DNA-seq on DNA isolated at baseline and upon progression
  - h) Plasma for ctDNA analysis to assess PIK3CA mutation status in response and resistance
- To assess the predictive effects of PIK3CA mutations and PTEN loss on PFS and CBR
  - To evaluate the ability of multi-parametric MRI performed early in therapy to predict both biological and clinical response.

### 3. BACKGROUND

#### 3.1 PI3K Pathway and Breast Cancer

Molecular alterations involving this pathway are considered the most frequent in breast cancer, encompassing over 30% of invasive tumors. PI3K is aberrantly activated in many human neoplasias. Alterations in breast cancer resulting in hyperactivity of the PI3K pathway include gain-of-function mutations in *PIK3CA* (the gene encoding the PI3K catalytic subunit p110 $\alpha$ ), mutations in *AKT1*, amplifications of *AKT2*, and loss of *PTEN*. Mutations in *PIK3CA* cluster in two major ‘hot spots’ located in the helical (E542K and E545K in exon 9) and catalytic (H1047R in exon 20) domains. Expression of these mutant p110 $\alpha$  isoforms confers growth factor-independent growth and protection from anoikis and chemotherapy. Loss of *PTEN* also increases PI3K activity and increased phosphorylation, activation, or membrane translocation of signal transducers downstream PI3K including Akt, mTOR, S6 kinase, and 4-EBP-1. Both genetic and biochemical data suggest that activation of the PI3K/Akt survival pathway contributes to breast cancer development and tumorigenesis.

Over the past decade, the term “triple negative breast cancer” has been used to classify tumors that lack expression of the estrogen receptor (ER), progesterone receptor (PR), and HER2. Triple negative breast cancers (TNBC) are generally more aggressive than their ER positive counterparts, with higher rates of relapse in the early stage and decreased overall survival in the metastatic setting. TNBC has been particularly difficult to treat given that the biology of the disease has not been well understood, thus molecular targets for therapeutic intervention are unknown. Recently, 104 TNBC exomes were sequenced and identified TP53 (62%) as the most frequently mutated gene, followed by alterations in PI3K pathway that included *PIK3CA* (10.2%) and *PTEN* (9.6%) mutations, suggesting that targeting the PI3K pathway would be clinically relevant in TNBC.

[figure not shown]
#### 3.2 Correlative Science Background

##### 3.2.1 PI3K pathway and triple negative breast cancer

Using gene expression (GE) analyses, we recently identified distinct TNBC subtypes displaying unique biologies. We identified six TNBC subtypes including two basal-like (BL1 and BL2), an immunomodulatory (IM), a mesenchymal (M), a mesenchymal stem-like (MSL), and a luminal androgen receptor (LAR) subtype. Further, GE analysis allowed us to identify TNBC cell lines representative of these subtypes. Predicted “driver” signaling pathways were pharmacologically targeted in these cell lines as proof-of-concept and to generate pre-clinical data to inform clinical trial design. The LAR subtype was characterized by androgen receptor signaling.

LAR cell lines were uniquely sensitive to inhibition of AR signaling achieved through siRNA-mediated AR knockdown or pharmacological inhibition by bicalutamide (an AR antagonist). From our initial analysis it was evident that all LAR cell lines analyzed had an activating PIK3CA mutation and were sensitive to PI3K inhibitors. The co-evolution of PIK3CA mutations with AR-dependency is similar to observations that ER-positive breast cancers frequently contain PIK3CA mutations. To confirm the enrichment of PIK3CA mutations in AR expressing TNBC, we isolated DNA from 26 LAR and 26 non-LAR TNBC tumors. Sanger sequencing was performed across exons 5 and 20 of amplified PIK3CA DNA from the same tumors as further validation. Seventy percent (18/26) of tumors of the LAR subtype contained activating ‘hotspot’ mutations in the PIK3CA gene.

AR+ tumors with a PIK3CA mutation expressed higher levels of activated p-AKT (S473). While PIK3CA mutations were detected in non-LAR TNBC (26.9%), the frequency of PIK3CA mutations was nearly double in LAR TNBC (70.0%), suggesting that these tumors may depend on PI3K and, as such, will be particularly sensitive to PI3K inhibitors. To determine the single agent effectiveness of cisplatin, bicalutamide and a PI3K inhibitor (GDC-0941), we performed viability assays evaluating the efficacy of these drugs across a panel of TNBC cell lines. Cell lines that possessed BRCA1/2 mutations and correlated to basal-like TNBC subtypes were especially sensitive to cisplatin (Figure 1A).

[figure not shown]

**Figure 1. TNBC subtypes display differential sensitivity to cisplatin, bicalutamide and GDC-0941.** IC50 values for cell lines 72 h after treatment with (A) cisplatin, (B) bicalutamide or (C) GDC-0941. Black, gray, and white color bars indicate TNBC subtype; white box with black dot indicates primary HMEC; pink, red, and blue color bars indicate mutation status for BRCA1/2, PIK3CA and PTEN, respectively. Heatmap below bicalutamide graph indicates levels of AR mRNA (Log2 GE).

As anticipated, AR+ TNBC cell lines were sensitive to the AR antagonist bicalutamide and the PI3K inhibitor GDC-0941 (Figure 1B and C). Since GDC-0941 displayed activity in PIK3CA mutant cell lines and all AR-expressing cell lines, we then sought to test the hypothesis that simultaneous targeting of AR and PI3K would be more effective than either agent alone. We genetically knocked down AR using shRNA in the presence of GDC-0941. Knockdown of AR significantly increased the efficacy of GDC-0941 over a range of doses as viability was reduced in the presence of two shRNAs targeting AR (Figure 2). We advanced the combination of these inhibitors to *in vivo* xenograft studies and examined bicalutamide ± GDC-0941; representative results are shown (Figure 2D).

To determine if pharmacological inhibition of AR with bicalutamide is more effective in combination with PIK3CA inhibition, we treated AR-expressing TNBC cells with either increasing doses of GDC-0941 or in combination with fixed doses of the inhibitor (10, 25, and 50  $\mu$ M) with bicalutamide. While increasing doses of bicalutamide alone decreased viability of each cell line, the combination with GDC-0941 was either additive or synergistic over a range of doses (1 -1000 nM) as measured by a viability assay (Alamar Blue detection). Bicalutamide treatment alone did not affect protein levels evaluated, however the combination with GDC-0941 decreased p-S6 more than GDC-0941 alone and decreased AR levels at 48 h.

**Figure 2. PI3K inhibition increases the efficacy of genetic and pharmacological targeting of AR in AR+ TNBC.** (A, upper) Immunoblots display decreased AR expression 72h after lentiviral infection with shRNAs targeting AR compared to control in indicated AR+ TNBC cell lines. (A, lower) Relative viability of LAR cell lines infected with nontargeting or shRNAs targeting AR (shAR1 and shAR2) after 72 h treatment with GDC-0941. (B) Relative viability of AR+ cell lines after indicated doses of GDC-0941 alone (blue) or in combination (red) with 25  $\mu$ M bicalutamide (CDX). Dashed black line depicts the theoretical line of additivity from the combined effect of bicalutamide and GDC-0941 alone. (C) Immunoblots show decreased pAKT and pS6 at 24 and 48 after treatment with 1  $\mu$ M GDC-0941 or the combination with 25  $\mu$ M CDX. (D) CAL-148 xenograft tumors display greater sensitivity to GDC-0941 and the combination compared to bicalutamide (CDX) alone. Mice were treated for approximately 3 weeks. Serial tumor volumes ( $\text{mm}^3$ ) were measured at the indicated days. Each data point represents the mean tumor volume of 16 tumors.

We tested the effectiveness of PI3K inhibition alone or in combination with bicalutamide in mice with CAL-148 xenograft tumors. GDC-0941 alone or in combination with bicalutamide significantly decreased the growth of CAL148 xenograft tumor growth. These results provide pre-clinical rationale for a clinical trial in which AR-positive triple negative breast cancer patients will receive a combination of an anti-androgen + a PI3K inhibitor.

### 3.3 Background on Study Treatment

#### 3.3.1 Taselisib

Taselisib is a potent, selective small-molecule inhibitor of Class I PI3K that is being developed by Genentech, Inc. as an anti-cancer therapeutic agent. Activating and transforming mutations in the p110 $\alpha$  subunit of PI3K are commonly found in tumors. The beta isoform of PI3K is involved in glucose metabolism, as evidenced by increased glucose levels in conditional p110 $\beta$  knockout mice compared with wild-type mice following a glucose challenge test. Taselisib has approximately 30-fold biochemical selectivity of the alpha isoform relative to the beta isoform and has been shown to be a potent inhibitor of growth in nonclinical models of PI3K-mutant tumors.

Refer to the tselisib Investigator's Brochure for further information regarding the nonclinical evaluation of tselisib.

##### 3.3.1.1 Summary of Clinical Data

As of 5 July 2013, a total of 144 patients have been treated with tselisib capsules, in the Phase I/II PMT4979g study, either as single agent (n = 90, 63%) or in combination with endocrine therapy (n = 54, 37%).

As of 5 July 2013, enrollment into the dose-escalation stage of Study PMT4979g had been completed with 34 patients enrolled at tselisib doses ranging from 3 to 16 mg daily. Tselisib was well tolerated in the first three cohorts (3, 5, and 8 mg), with no patients experiencing a dose-limiting toxicity (DLT). At the 16-mg dose level, 2 of the 11 safety-evaluable patients experienced a DLT (Grade 4 hyperglycemia and Grade 3 fatigue). At the 12-mg dose level, 1 of the 10 safety-evaluable patients experienced a DLT of Grade 3 acute renal failure. Although the single-agent tselisib maximum tolerated dose (MTD) was not exceeded at the 16-mg dose level, the recommended tselisib dose and schedule for the single-agent expansion cohorts is 9 mg daily on the basis of long-term safety data through multiple treatment cycles. As of the cutoff date, a total of 53 patients had been enrolled in the 9-mg daily dosing expansion cohorts.

As of 5 July 2013, adverse events of any grade that occurred in  $\geq 10\%$  of the 87 patients treated with daily single-agent tselisib capsules and were investigator-assessed as related to tselisib were as follows: diarrhea (47%), hyperglycemia (38%), nausea (36%), fatigue (35%), decreased appetite (31%), rash (25%), stomatitis (13%), vomiting (13%), and mucosal inflammation (11.5%). Grade 3 and 4 adverse events assessed by the investigator as tselisib related included hyperglycemia (12%), colitis (6%), rash (5%), diarrhea (3%), fatigue (3%), pneumonitis (3%), pruritus (2%), stomatitis (2%), increased alanine aminotransferase levels (1%), anemia (1%), increase in blood creatinine (1%), exfoliative rash (1%), hypokalemia (1%), hypophosphatemia

(1%), lung infection (1%), pneumonia (1%), erythematous rash (1%), generalized rash (1%), maculopapular rash (1%) and skin exfoliation (1%) and acute renal failure (1%).

As of 5 July 2013, a total of 27 patients have been enrolled in the expansion cohort of taselisib at dose levels of 6 and 9 mg daily (19 patients at 6 mg, and 8 patients at 9 mg) daily in combination with letrozole (Cohort E). No DLTs were observed at either dose level. Adverse events of any grade and assessed by the investigator as drug related that occurred in  $\geq 10\%$  of the 27 safety-evaluable patients assessed as related to taselisib were diarrhea (67%), fatigue (30%), nausea (30%), rash (30%), decreased appetite (26%), hyperglycemia (26%), stomatitis (26%), dysgeusia (22%), mucosal inflammation (19%), asthenia (15%), pruritis (15%), vomiting (15%) and dry mouth (11%). Grade 3 and 4 adverse events assessed by the investigator as taselisib related include diarrhea (11%), mucosal inflammation (7%), increased amylase (4%), hyperglycemia (4%), increased aspartate aminotransferase (AST) (4%), stomatitis (3.7%), increased blood alkaline phosphate (4%), fatigue (4%), increased gamma-glutamyltransferase in the blood (4%), hypokalemia (4%), increased lipase in the blood (4%) and papilloedema (4%).

As of 5 July 2013, a total of 27 patients have been enrolled in the expansion cohort of taselisib at dose levels of 6 and 9 mg daily (21 patients at 6 mg and 6 patients at 9 mg) in combination with fulvestrant (Cohort F). No DLTs were observed at either dose level. One patient has been enrolled in the Phase II part of the study with 6 mg taselisib in combination with fulvestrant. Adverse events assessed by the investigator as taselisib related and of any grade that occurred in  $\geq 10\%$  of the 27 patients and were assessed as related to taselisib were diarrhea (48%), hyperglycemia (33%), nausea (33%), decreased appetite (26%), fatigue (26%), rash (26%), stomatitis (22%), asthenia (19%), muscle spasms (15%), vomiting (15%), dysgeusia (11%), gastroesophageal reflux disease (11%) and mucosal inflammation (11%). Grade 3 and 4 adverse events assessed by the investigator as related to taselisib included hyperglycemia (15%), diarrhea (7%), dyspnea (4%), flank pain (4%), hyponatremia (4%), neutropenia (4%), rash (4%) and vomiting (4%). A phase 1b study of taselisib in combination with paclitaxel is ongoing.

Refer to the taselisib Investigator's Brochure for further information regarding the nonclinical and clinical safety evaluation of taselisib.

### 3.3.2 Enzalutamide

Enzalutamide (Medivation) is approved by the United States Food and Drug Administration (FDA) for the treatment of men with metastatic castrate resistant prostate cancer (CRPC) who previously received docetaxel. Enzalutamide is marketed as Xtandi and was formerly known as MDV3100. Enzalutamide is an androgen receptor antagonist which acts by competitively inhibiting (1) testosterone binding to androgen receptors, (2) nuclear translocation of androgen receptors, and (3) DNA binding and activation by androgen receptors. Enzalutamide is administered orally.

Refer to the Enzalutamide Investigator's Brochure for further information regarding the nonclinical evaluation of Enzalutamide.

### 3.3.2.1 Summary of Clinical Data

Enzalutamide has been studied primarily in patients with prostate cancer. The pharmacokinetics (PK), tolerability, and antitumor activity of enzalutamide (then known as MDV3100) were first studied in a multicenter, open-label, first-in-human, dose-escalation study in 140 patients with CRPC. Patients who were chemotherapy-naïve or who had previous docetaxel-based chemotherapy failure were treated with enzalutamide at doses of 30 to 600 mg/day until disease progression or intolerable side effects developed. The maximum tolerated dose was determined to be 240 mg daily. After review of all data available from S-3100-1-01, the optimal dose of enzalutamide for evaluation in phase 3 clinical trials was determined to be 160 mg/day. AFFIRM was a phase 3, randomized, double-blind, placebo-controlled, efficacy and safety study of enzalutamide (160 mg daily) in patients with progressive CRPC previously treated with docetaxel-based chemotherapy which was conducted in 1199 men, 800 of whom received treatment with enzalutamide. The primary endpoint was overall survival. The FDA approval of enzalutamide was based on the results of this study. PREVAIL was a multinational, phase 3, randomized, double-blind, placebo-controlled, efficacy and safety study of enzalutamide in chemotherapy-naïve patients with progressive metastatic prostate cancer and prior androgen deprivation failure. Subjects included 1717 men, approximately half of whom received treatment with enzalutamide. The interim analysis at 539 deaths showed a statistically significant benefit of enzalutamide over placebo with a 30% reduction in risk of death (OS: HR 0.70; 95% CI: 0.59-0.83; P< 0.0001) and an 81% reduction in risk of radiographic progression or death (rPFS: HR 0.19; 95% CI: 0.15-0.23; P< 0.0001). At the time of the analysis, 28% of enzalutamide patients and 35% of placebo patients had died. Estimated median OS was 32.4 months (95% CI, 31.5–upper limit not yet reached) in the enzalutamide arm vs 30.2 mo (95% CI, 28–upper limit not yet reached) in the placebo arm. Median rPFS was not yet reached in the enzalutamide arm vs 3.9 mo (95% CI: 3.7-5.4) in the placebo arm. Seizure events were reported in two patients. The Independent Data Monitoring Committee considered the benefit-risk ratio to favor enzalutamide and recommended stopping the study and crossing placebo patients to enzalutamide. Protocol MDV3100-11 is evaluating single agent enzalutamide in women with triple negative breast cancer that is androgen receptor positive. Two other protocols with enzalutamide in breast cancer are ongoing: (1) MDV3100-12, investigating exemestane plus enzalutamide or placebo in hormone-receptor positive breast cancer and (2) 9785-CL-1121, investigation enzalutamide with trastuzumab in HER2+ AR+ metastatic breast cancer. More than 4200 subjects and patients have been enrolled worldwide in completed and ongoing clinical trials evaluating enzalutamide. The cumulative exposure to enzalutamide is estimated to be more than 2900 subjects and patients who received at least 1 dose in any clinical study as of January 2013.

### 3.4 Rationale

Therapies for breast cancer should be guided by biologic features of the tumor, such as expression of steroid hormone receptors and hormone dependence and/or HER2/neu overexpression. Notable examples are the successful use of hormonal therapy (e.g. tamoxifen or aromatase inhibitors) for patients with hormone-sensitive (estrogen receptor [ER] and/or progesterone receptor [PR] expressing) tumors, and the use of trastuzumab (HerceptinTM), a monoclonal antibody against HER2/neu, for patients with overexpression of the aforementioned protein. These are excellent examples of where appropriate patient selection is instrumental on the success of these therapies. An unfortunate problem triple negative breast cancer is that the key drivers of this disease are not well understood, and thus molecular targets for therapeutic intervention have not been identified.

We have identified distinct subtypes of triple negative breast cancer to better understand potential drivers of disease progression and to help identify potential therapeutic targets. Considering all of our preclinical data, we propose a clinical trial in which patients with metastatic TNBC have their tumor tissue initially assessed for androgen receptor (AR) status by standard CLIA-certified AR IHC analysis. For patients who are AR positive, we propose a phase Ib/II study of enzalutamide +/- taselisib. We hypothesize that the combination of enzalutamide + taselisib will provide an improvement in outcome compared to enzalutamide alone. This study will elucidate the safety and preliminary therapeutic value of this combination.

## 4. PARTICIPANT SELECTION

### 4.1 Inclusion criteria

- 4.1.1 Patients must provide informed written consent.
- 4.1.2 Patients must be  $\geq 18$  years of age.
- 4.1.3 ECOG performance status 0-1.
- 4.1.4 Clinical stage IV invasive mammary carcinoma
- 4.1.5 For phase 1b: HER2 negative, as defined for phase II. Any ER/PR (negative or positive) can be enrolled in the phase 1b portion. For phase II: ER negative (defined as expression of ER in  $\leq 5\%$  cells), PR negative (defined as expression of PR in  $\leq 5\%$  cells), HER2 negative [acceptable methods of HER2 analysis include IHC (0, 1+), fluorescence in situ hybridization (FISH) with HER2/CEN-17 ratio  $< 2$ , and/or chromogenic in situ hybridization (CISH) with HER2/CEN-17 ratio  $< 2$ ], as previously documented by histological analysis.
- 4.1.6 Androgen receptor positivity, defined as  $\geq 10\%$  of tumor cell nuclei with immunoreactivity for AR on central review at Vanderbilt.

- 4.1.7** Measurable or evaluable disease. Measurable disease is defined as at least one lesion that can be accurately measured in at least one dimension by RECIST criteria 1.1, with radiologic scans within 28 days of day 1, cycle 1. Evaluable disease must include bone metastases (pleural effusions and ascites are not considered evaluable for this study).
- 4.1.8** Any number of prior therapies as long as patients have adequate performance status and meet all other eligibility criteria.
- 4.1.9** Prior treatment with anti-androgens other than enzalutamide is acceptable.
- 4.1.10** Phase 1b only: FFPB or fresh frozen tissue from the original diagnosis or the metastatic setting should be located. Tissue must be submitted with 3 weeks of study initiation.
- 4.1.11** Phase II only: Biopsy of a metastatic lesion in patients with reasonably accessible metastatic lesions (chest wall, skin, subcutaneous tissue, lymph nodes, skin, breast, bones, lung, and liver metastases). If a reasonably accessible metastatic lesion is not available, the patient may go on study provided that archived tissue is available. However, if a reasonably accessible site is available for biopsy, the patient must agree to biopsy. Any patients not undergoing biopsy must be approved for study enrollment by the Protocol Chair. Biopsies may be done with local anesthesia or intravenous conscious sedation, according to institutional guidelines. If a biopsy requires general anesthesia, then it is only allowed if acquisition of tissue is clinically indicated, and excess tissue may be collected for research purposes. Patients without sites available for biopsy must have available tissue [archived formalin-fixed paraffin embedded blocks (FFPB) or fresh frozen tissue from original diagnosis or metastatic setting] for correlative studies per Section 9.2.

Tissue needs to be located and available at the time of registration (tissue needs to be submitted within 3 weeks of study initiation).

**4.1.12** Patients must have adequate hematologic, hepatic, and renal function. All tests must be obtained within 28 days of starting treatment. Labs are to be repeated on C1D1 and must still meet eligibility. These include:

- ANC  $\geq 1500/\text{mm}^3$
- Platelet count  $\geq 75,000/\text{mm}^3$
- HgB  $\geq 9$  g/dL
- Creatinine  $\leq 1.5X$  upper limits of normal (ULN)
- INR  $\leq 2$
- Total serum bilirubin  $\leq 1.5$  x ULN (in patients with known Gilbert Syndrome, a total bilirubin  $\leq 3.0$  x ULN, with direct bilirubin  $\leq 1.5$  x ULN)
- AST and ALT  $\leq 3$  x ULN (or  $\leq 5.0$  x ULN if hepatic metastases are present)
- For patients without known Type II diabetes, the following is required at screening:
  - Fasting plasma glucose  $\leq 160$  mg/dL (7.49 mmol/L) and glycosylated hemoglobin (HbA1c)  $< 7.5$  % or International Federation of Clinical Chemistry (IFCC)  $< 53$  mmol/mol
- For patients with Type II diabetes receiving only oral anti-hyperglycemic therapy (patients receiving insulin are not eligible), the following are required at screening:
  - HbA1c  $< 8.5$  % or IFCC  $< 69.4$  mmol/mol
  - Stable regimen of oral anti-hyperglycemic therapy without insulin usage for at least 3 weeks prior to first study treatment
  - Fasting plasma glucose levels  $\leq 160$  mg/dL (8.88 mmol/L) and no hypoglycemia (BS  $< 60$ ) during home monitoring for at least 1 week prior to study entry

**4.1.13** Patients must be able to swallow and retain oral medication.

**4.1.14** For patients who are not postmenopausal or surgically sterile (absence of ovaries and/or uterus), agreement to remain abstinent or to use two adequate methods of contraception (e.g., condoms, diaphragm, vasectomy/vasectomized partner, tubal ligation), during the treatment period and for at least 30 days after the last dose of study treatment or 3 months after discontinuation of taselisib and/or enzalutamide, whichever is longer. Hormone based oral contraceptives are not allowed on study. Postmenopausal is defined as:

- Age  $\geq 60$  years
- Age  $\leq 60$  years and amenorrheic for 12 months in the absence of chemotherapy, tamoxifen, toremifene, or ovarian suppression; or follicle stimulating hormone and estradiol in the postmenopausal range

**4.1.15** Patients may have received radiation therapy to painful bone metastases or areas of impending bone fracture as long as radiation therapy is completed  $\geq 2$  weeks prior to day 1 of cycle 1 of treatment. Patients who have received prior radiotherapy must have recovered from toxicity ( $\leq$  grade 2) induced by this treatment. Baseline radiologic scans must be obtained after completion of radiation.

**4.1.16** Patients must complete all screening assessments as outlined in the protocol.

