Endocrine: Hyperglycemia	
 
• Hyperglycemia Grade 3 (FPG 250 – 399 mg/dL; 13.9 - 22.2 mmol/L) (confirmed with a repeat FPG within 24 hrs) for > 7 consecutive days despite oral anti-diabetic treatment
 
• Hyperglycemia Grade 4 (FPG ≥ 400 mg/dL; ≥ 22.3 mmol/L)
 
• Hyperglycemia leading to diabetic keto-acidosis, hospitalization for IV insulin infusion, or non-ketotic coma
 
• Hyperglycemia occurring during corticosteroid administration will be only considered DLT if not resolved within 2 days after the end of corticosteroid treatment.
 
	
For details of the follow-up and treatment of ≥ grade 3 hyperglycemia refer to the Guidelines for the treatment of study drug-induced hyperglycemia provided in the Dose Modification Section

GI disorders	
 
• Diarrhea CTCAE Grade ≥ 3 for ≥ 48 hrs, despite the use of optimal anti-diarrhea therapy
 
• Nausea/vomiting CTCAE Grade ≥ 3 for ≥ 48 hrs, despite the use of optimal anti-emetic therapy
 
• Pancreatitis CTCAE Grade ≥ 3
 
	
If amylase and/or lipase ≥ CTCAE grade 3 (> 2 x ULN) has been demonstrated, these parameters must be assessed once at 2 to 4 days and once again at 7 days (± 1 day) and be repeated twice a week until resolution to ≤ CTCAE grade 2 to allow for initiation of re-treatment, and then at least weekly until either resolution to ≤ CTCAE grade 1 or until stabilization.
 
A CT scan or other imaging study to assess the pancreas, liver, and gallbladder must be performed within 1 week of the first occurrence of any ≥ CTCAE grade 3 of amylase or lipase. Amylase and lipase should be followed weekly until resolution to ≤ CTCAE grade 1.

Table 1: DLT criteria and Follow-up Evaluation (CTCAE v 4.0)		
Toxicity	DLT criteria	Follow-Up Evaluation

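### Inclusion criterion 4.1.12 prints the same fasting glucose limit, 160 mg/dL, as 7.49 mmol/L for one patient group and 8.88 mmol/L for another; the HbA1c pair has a similar but narrower mismatch

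*Combined protocol and SAP*

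**What the plan says.** Section 4.1.12 sets glucose and HbA1c limits separately for two groups.

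- **No known diabetes.** The bullet opens "For patients without known Type II diabetes, the following is required at screening". Fasting plasma glucose must be at most 160 "mg/dL (7.49 mmol/L) and glycosylated hemoglobin (HbA1c", with HbA1c below 7.5%. The alternative HbA1c unit is introduced by "or International Federation of Clinical Chemistry (IFCC", with a limit of 53 mmol/mol.
- **Type II diabetes on oral therapy only.** HbA1c must be below 8.5% "or IFCC $< 69.4$ mmol/mol", and fasting plasma glucose at most 160 "mg/dL (8.88 mmol/L) and no hypoglycemia" during home monitoring.

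The stem of the criterion adds: "Labs are to be repeated on C1D1 and must still meet eligibility". The study calendar schedules fasting glucose at screening and C1D1 but HbA1c at screening only. Section 6.6 requires crossover patients to meet the inclusion values again before taselisib. Fasting glucose is in the crossover calendar; HbA1c is not, and section 6.6 exempts tests outside that calendar from repetition.

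The DLT table in section 6.2.2 gives glucose in both units: "Hyperglycemia Grade 3 (FPG 250 – 399 mg/dL; 13.9 - 22.2 mmol/L", with grade 4 starting at 400 mg/dL or 22.3 mmol/L.

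**The concern.** An eligibility limit printed in two units should be one limit. Here the same mg/dL figure has two mmol/L figures inside a single criterion, so at least one pair is wrong. Because the mmol/L value stands in parentheses, it reads as an equivalent of the mg/dL value and not as a separate limit. Whoever compares a laboratory report with the criterion can reach opposite decisions on the same patient, depending on the unit.

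The intended rule cannot be recovered from the text. In mg/dL the two groups share one glucose limit; in mmol/L the limit is stricter for patients without known diabetes. The glucose limit is also used more than once: at screening, on C1D1, and before crossover taselisib. The HbA1c pair for the same group raises a similar question, with less reach.

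**Working it through.** **1. The protocol's own glucose factor (mg/dL divided by mmol/L)**

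| Place | Pair | Factor |
|---|---|---|
| 6.2.2, grade 3 lower bound | 250 / 13.9 | 17.99 |
| 6.2.2, grade 3 upper bound | 399 / 22.2 | 17.97 |
| 6.2.2, grade 4 | 400 / 22.3 | 17.94 |
| 4.1.12, Type II diabetes | 160 / 8.88 | 18.02 |
| 4.1.12, no known diabetes | 160 / 7.49 | 21.36 |

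Four of the five pairs agree on about 18. Only the limit for patients without known diabetes departs.

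**2. Conversion of the discrepant pair**

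With the usual factor of 18.016:
- 160 / 18.016 = 8.88 mmol/L, which reproduces the Type II diabetes figure.
- 7.49 × 18.016 = 134.9 mg/dL.

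The result does not depend on that constant. Over the protocol's own range of 17.94 to 18.02, 160 mg/dL is 8.92 to 8.88 mmol/L, and 7.49 mmol/L is 134.4 to 135.0 mg/dL.

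The discordant band is above about 135 and up to 160 mg/dL, a width of about 160 − 135 = 25 mg/dL. Example: 150 mg/dL is 150 / 18.016 = 8.33 mmol/L, which is within 160 mg/dL but above 7.49 mmol/L.

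**3. HbA1c**

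Assumption: the standard NGSP-to-IFCC line, IFCC = 10.929 × (% − 2.15). The protocol does not print it.
- Check on the Type II diabetes pair: 10.929 × (8.5 − 2.15) = 69.4 mmol/mol, as printed.
- No known diabetes: 10.929 × (7.5 − 2.15) = 58.5 mmol/mol, against 53 printed.
- In reverse: 53 / 10.929 + 2.15 = 7.0%.

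The two printed pairs imply a slope of (69.4 − 53) / (8.5 − 7.5) = 16.4 mmol/mol per percentage point, against 10.929. The discordant band is from about 7.0% to below 7.5%. Example: 7.2% is 10.929 × (7.2 − 2.15) = 55.2 mmol/mol.

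**4. Where each limit is applied**

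| Time | Glucose | HbA1c |
|---|---|---|
| Screening | yes | yes |
| C1D1 | yes | not scheduled |
| Before crossover taselisib | yes | not scheduled |

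**The case against.** The glucose contradiction has no good answer. The objections bear on how far the point extends, and four of them stand.

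- **HbA1c.** A reader might infer that HbA1c eligibility contradicts itself in the same way. The documents do not support that. The two HbA1c figures are joined by *or*, so on a literal reading a patient at 7.2% qualifies on the percentage alone. The mismatch also needs a formula that the protocol does not print; the 8.5% pair fits it, but one pair cannot fix both slope and intercept.
- **Repeat testing.** A reader might infer that both limits are re-applied on C1D1. Only glucose is scheduled then.
- **Safety.** A reader might infer that the error lets patients at undue risk onto a drug known to cause hyperglycemia. The SI figures are the stricter ones, so using them admits nobody above the mg/dL or percentage limits. Even the looser reading is no looser than what the protocol accepts in Type II diabetes: the same 160 mg/dL and a higher HbA1c. Section 3.3.1.1 reports taselisib-related grade 3 and 4 hyperglycemia of 12% on single agent, 4% with letrozole and 15% with fulvestrant, in a study with dose-escalation levels of 3 to 16 mg and combination cohorts at 6 and 9 mg. Phase II here uses 4 mg. Those rates show why glucose is screened; they do not measure the effect of this error.
- **Practice.** A reader might infer that sites are applying different criteria. No section states reporting units or identifies a site using mmol/L or IFCC units. The mg/dL and percentage figures come first throughout, and section 5.4 has the coordinating center check eligibility from source documents before registration.

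None of this removes the glucose problem. A central check limits divergence between sites, but it does not tell the checker which printed figure governs.

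**Conclusion.** The glucose limit for patients without known Type II diabetes is wrong as written, and the documents prove it without any outside figure. The same 160 mg/dL has two SI values in one criterion, and the pair with 7.49 mmol/L departs from the factor of about 18 used elsewhere. Eligibility is contradictory for glucose above about 135 and up to 160 mg/dL at screening, on C1D1 and before crossover taselisib.

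The HbA1c mismatch is secondary. It rests on the assumed NGSP-IFCC line and matters only at screening, where the two figures are read as equivalents or only IFCC units are reported.

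The practical effect is limited to patients inside these bands and to use of the SI figures. The documents give no basis for counting such patients. The Simon two-stage design, the sample size and the error rates are untouched. The arithmetic shows that the pairs disagree; it does not show whether the conventional or the SI figure was intended.

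**What to change.** Reconcile each pair in section 4.1.12 so that both units express one limit, or keep a single unit for each test. The sponsor must state which glucose limit and which HbA1c limit is intended for patients without known Type II diabetes; no threshold is proposed here. If both HbA1c units are kept, say whether they are equivalents or true alternatives. Carry the change into the eligibility checklist if it has the same figures (the checklist is not in the documents).

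The cost is a correction to two pairs of figures, with no change to the design or the analysis. If patients were already screened using SI units, a check of those in the two bands would show whether any decision turned on the discrepancy.
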